Appendix F Abbreviations

Abbreviation	Explanation
A _{2A} R	Adenosine 2a receptor
ADA	Anti-drug antibody
AE	Adverse event (see definition in Appendix B)
AESI	Adverse event of special interest
ALP	Alkaline phosphatase
ALT	Alanine aminotransferase
AST	Aspartate aminotransferase
AUC	Area under the concentration-time curve
BCRP	Breast cancer resistance protein
BP	Blood pressure
CD73	Cluster of differentiation 73: 5'-nucleotidase (5'-NT) or ecto-5'-nucleotidase
CI	Confidence interval
C _{max}	Maximum observed concentration
CNS	Central nervous system
CR	Complete response
CRP	C-reactive protein
CSR	Clinical study report
CT	Computed tomography
CTCAE	Common Terminology Criteria for Adverse Events
CCI	CCI
CYP	Cytochrome P450
DCO	Data cut-off
DILI	Drug induced liver injury
DLT	Dose-limiting toxicity
ECG	Electrocardiogram
ECHO	Echocardiogram
ECOG	Eastern Cooperative Oncology Group
eCRF	Electronic case report form
EGFR	Epidermal growth factor receptor
EOT	End of treatment (visit)
FDA	Food and Drug Administration
FDG-PET	Fluorodeoxyglucose positron emission tomography
FTIH	First-time-in-human
GCP	Good Clinical Practice

Abbreviation	Explanation
GGT	Gamma glutamyltransferase
HL	Hy's Law
IATA	International Air Transport Association
IB	Investigator's brochure
IC ₅₀	Concentration giving 50% of the drug-induced inhibitory effect
ICF	Informed consent form
ICH	International Council for Harmonisation
IEC	Independent ethics committee
CCI	CCI
ILD	Interstitial lung disease
imAE	Immune-mediated adverse event
IP	Investigational product
IRB	Institutional Review Board
CCI	CCI
IV	Intravenous
IWRS	Interactive web response system
LDH	Lactate dehydrogenase
mAb	Monoclonal antibody
MATE1	Multidrug and toxin extrusion protein 1
mCRPC	Metastatic castration-resistant prostate carcinoma
MDSC	Myeloid-derived suppressor cells
MOA	Mechanism of action
MRI	Magnetic resonance imaging
MTD	Maximum-tolerated dose
MUGA	Multigated acquisition scan
NCI	National Cancer Institute
NE	Not evaluable
NHA	New hormonal agent(s)
NSCLC	Non-small cell lung cancer
NTL	Non-target lesion
OAT1	Organic anion transporter 1
OATP	Organic anion transporter polypeptide
OCT	Organic cation transporter
ORR	Overall response rate
CCI	CCI

Abbreviation	Explanation
PBMC	Peripheral blood mononuclear cells
PCWG3	Prostate Cancer Working Group 3
PD	Progression of disease
PD-1	Programmed cell death protein 1 (e.g., nivolumab [Opdivo®])
PD-L1	Programmed death ligand 1
CCI	CCI
PDx	Pharmacodynamics
PET	Positron emission tomography
PFS	Progression-free survival
P-gp	P-glycoprotein
PHL	Potential Hy's Law
PK	Pharmacokinetics
PO	Per os (orally)
PR	Partial response
PSA	Prostate-specific antigen
Q2W	Every 2 weeks
Q4W	Every 4 weeks
QD	Once daily
QRS	QRS complex; the main spike on an ECG line
QT	ECG interval measured from the onset of the QRS complex to the end of the T wave
QTc	QT interval corrected for heart rate
QTcF	QT interval corrected for heart rate using Fridericia's formula
RECIST	Response Evaluation Criteria in Solid Tumors
RP2D	Recommended Phase 2 dose
rPFS	Radiographic progression-free survival
SAE	Serious adverse event (see definition in Appendix B)
SD	Stable disease
SoA	Schedule of activities
SRC	Safety Review Committee
TBL	Total bilirubin
TBNK	Complete immune panel (T-, B-, and natural killer [NK] lymphocyte subsets)
TL	Target lesion
t _{max}	Time to reach C _{max}
TME	Tumor microenvironment
ULN	Upper limit of normal

Appendix G Guidelines for Evaluation of Objective Tumor Response Using RECIST Version 1.1 (Response Evaluation Criteria in Solid Tumors) in Soft Tissue and PCWG3 (Prostate Cancer Working Group Criteria 3) in Bone Lesions

INTRODUCTION

This appendix details the implementation of RECIST (Response Evaluation Criteria in Solid Tumors) 1.1 guidelines (Eisenhauer et al. 2009) and PCWG3 guidelines (Scher et al. 2016) for the D8731C00001 study with regards to Investigator assessment of tumor burden including protocol-specific requirements for this study.

ASSESSMENT OF SOFT TISSUE DISEASE USING RECIST 1.1 CRITERIA

Definition of measurable, non-measurable, target and non-target lesions

Patients with at least one lesion (measurable and/or non-measurable) that can be accurately assessed at baseline by computed tomography (CT), magnetic resonance imaging (MRI) or plain X-ray should be included in this study.

Measurable:

A lesion, not previously irradiated, that can be accurately measured at baseline as ≥ 10 mm in the longest diameter (except lymph nodes which must have short axis ≥ 15 mm) with computed tomography (CT) or magnetic resonance imaging (MRI) and which is suitable for accurate repeated measurements.

Non-measurable:

- All other lesions, including small lesions (longest diameter <10 mm or pathological lymph nodes with ≥ 10 to <15 mm short axis at baseline*).
- Truly non-measurable lesions include the following: leptomeningeal disease, ascites, pleural / pericardial effusion, inflammatory breast disease, lymphangitic involvement of skin or lung, abdominal masses/abdominal organomegaly identified by physical examination that is not measurable by CT or MRI.
- Previously irradiated lesions**.
- Skin lesions
- Brain metastasis

*Nodes with <10 mm short axis are considered non-pathological and should not be recorded or followed as NTL.

****Localized post-radiation changes which affect lesion sizes may occur. Therefore, lesions that have been previously irradiated will not be considered measurable and must be selected as Non-Target Lesions (NTL) at baseline and followed up as part of the NTL assessment.**

Special Cases:

- Lytic bone lesions or mixed lytic blastic lesions, with identifiable soft tissue components, can be considered measurable if the soft tissue component meets the definition of measurability. Blastic lesions are considered non-measurable.
- Cystic metastases can be considered measurable lesions if they meet the criteria for measurability from a radiological point of view, but if non-cystic lesions are present in the same subject, these should be selected as target lesions.

Target lesions:

A maximum of 5 measurable lesions (with a maximum of 2 lesions per organ), representative of all lesions involved suitable for accurate repeated measurement, should be identified as target lesions (TL) at baseline.

Non-Target lesions:

All other lesions (or sites of disease) not recorded as TL should be identified as NTL at baseline (except bone lesions which will be assessed as defined in bone lesion section of this appendix).

Methods of assessment

The same method of assessment and the same technique should be used to characterize each identified and recorded lesion at baseline and during follow-up visits.

A summary of the methods to be used for RECIST assessment is provided below and those excluded from tumor assessments for this study are highlighted, with the rationale provided.

Table 11 Summary of Methods of Assessment

Target Lesions	Non-Target Lesions	New Lesions
CT (preferred)	CT (preferred)	CT (preferred)
MRI	MRI	MRI
	X-ray, Chest x-ray	X-ray, Chest x-ray
		Ultrasound
		FDG-PET

CT and MRI

CT and MRI are generally considered to be the best currently available and reproducible methods to measure TL selected for response assessment and to assess NTL and identification of any new lesions.

In the D8731C00001 study it is recommended that CT examinations of the chest, abdomen and pelvis will be used to assess tumor burden at baseline and follow-up visits. CT examination with intravenous (i.v.) contrast media administration is the preferred method. MRI should be used where CT is not feasible or it is medically contra-indicated.

Every effort should be made to maintain the radiologic imaging modality used at baseline throughout subsequent assessments.

X-rays

Plain X-rays

Plain X-rays may be used as a method of assessment for bone NTLs and to identify the presence of new bone lesions.

Chest X-ray

In the D8731C00001 study, chest x-ray assessment will not be used for assessment of TL as they will be assessed by CT examination or MRI examination. Chest X-ray can, however, be used to assess NTL and to identify the presence of new lesions.

Ultrasound

In the D8731C00001 study, ultrasound examination will not be used for assessment of TL and NTL as it is not a reproducible method, does not provide an accurate assessment of tumor size and it is subjective and operator dependent. Ultrasound examination can, however, be used to identify the presence of new lesions. If new clinical symptoms occur and an ultrasound is performed then new lesions should be confirmed by CT or MRI examination.

Endoscopy and laparoscopy

In the D8731C00001 study, endoscopy and laparoscopy will not be used for tumor assessments as they are not validated in the context of tumor assessment.

CCI

CCI

CCI

Cytology and histology

In the D8731C00001 study histology will not be used for tumor response assessments as per RECIST 1.1 and tumor response assessments will be performed on radiological criteria only.

FDG-PET scan

In the D8731C00001 study FDG-PET scans may be used as a method for identifying new lesions, according with the following algorithm: New lesions will be recorded where there is positive FDG uptake* not present on baseline FDG-PET scan or in a location corresponding to a new lesion on CT/MRI at the same follow-up visit. If there is no baseline FDG-PET scan available, and no evidence of new lesions on CT/MRI scans then follow-up CT/MRI assessments should be continued, scheduled as per protocol or clinical indicated, in order to confirm new lesions.

* A positive FDG-PET scan lesion should be reported only when an uptake greater than twice that of the surrounding tissue is observed.

Tumor response evaluation

Schedule of evaluation

Baseline assessments should encompass all areas of known predilection for metastases in the disease under evaluation and should additionally investigate areas that may be involved based on signs and symptoms of individual subjects and should be performed no more than 28 days before allocation/randomization. The first follow-up assessment for Modules 1, 2, and 3 should be initially at 6 weeks (± 1 week) following the start of AZD4635 dosing and subsequent assessments will be performed every 2 cycles (8 weeks, ± 1 week) thereafter. Any other sites at which new disease is suspected should also be adequately imaged at follow-up.

If an unscheduled assessment was performed and the subject has not progressed, every attempt should be made to perform the subsequent assessments at their originally scheduled visits. This schedule is to be followed in order to minimize any unintentional bias caused by some subjects being assessed at a different frequency than other subjects.

Target lesions (TL)

Documentation of target lesions

A maximum of 5 measurable lesions, with a maximum of 2 lesions per organ (including lymph nodes), representative of all lesions involved should be identified as TL at baseline.

Target lesions should be selected on the basis of their size (longest diameter for non-nodal lesions or short axis for nodal lesions), but in addition should be those that lend themselves to reproducible repeated measurements. It may be the case that, on occasion, the largest lesion does not lend itself to reproducible measurement in which circumstance the next largest lesion, which can be measured reproducibly, should be selected.

The site and location of each TL should be documented as well as the longest diameter for non-nodal lesions (or short axis for lymph nodes). All measurements should be recorded in millimeters. At baseline the sum of the diameters for all TL will be calculated and reported as the baseline sum of diameters. At follow-up visits the sum of diameters for all TL will be calculated and reported as the follow-up sum of diameters.

Special cases:

- For TL measurable in 2 or 3 dimensions, always report the longest diameter. For pathological lymph nodes measurable in 2 or 3 dimensions, always report the short axis.
- If the CT/MRI slice thickness used is > 5mm, the minimum size of measurable disease at baseline should be twice the slice thickness of the baseline scan.
- If a lesion has completely disappeared, the longest diameter should be recorded as 0 mm.
- If a TL splits into 2 or more parts, then record the sum of the diameters of those parts.
- If 2 or more TL merge then the sum of the diameters of the combined lesion should be recorded for one of the lesions and 0 mm recorded for the other lesion(s).
- If a TL is believed to be present and is faintly seen but too small to measure, a default value of 5mm should be assigned. If an accurate measure can be given, this should be recorded, even if it is below 5mm.
- If a TL cannot be measured accurately due to it being too large, provide an estimate of the size of the lesion.
- When a TL has had any intervention e.g., radiotherapy, embolization, surgery etc., during the study, the size of the TL should still be provided where possible.

Evaluation of target lesions

This section provides the definitions of the criteria used to determine objective tumor visit response for TL.

Table 12 Evaluation of target lesions

Complete Response (CR)	Disappearance of all target lesions since baseline. Any pathological lymph nodes selected as target lesions must have a reduction in short axis to < 10 mm.
Partial Response (PR)	At least a 30% decrease in the sum of the diameters of TL, taking as reference the baseline sum of diameters

Table 12 Evaluation of target lesions

Stable Disease (SD)	Neither sufficient shrinkage to qualify for PR nor sufficient increase to qualify for PD
Progressive Disease (PD)	At least a 20% increase in the sum of diameters of target lesions, taking as reference the smallest sum on study (this includes the baseline sum if that is the smallest on study). In addition to the relative increase of 20%, the sum must also demonstrate an absolute increase of at least 5 mm.
Not Evaluable (NE)	Only relevant if any of the target lesions were not assessed or not evaluable or had a lesion intervention at this visit. Note: If the sum of diameters meets the progressive disease criteria, progressive disease overrides not evaluable as a target lesion response

Non-Target lesions (NTL)

Evaluation of non-target lesions

All other lesions (or sites of disease), except for bone lesions, not recorded as TL should be identified as NTL at baseline. Measurements are not required for these lesions, but their status should be followed at subsequent visits. At each visit an overall assessment of the NTL response should be recorded by the Investigator. This section provides the definitions of the criteria used to determine and record overall response for NTL at the investigational site at each visit.

Table 13 Evaluation of Non-Target Lesions

Complete Response (CR)	Disappearance of all non-target lesions since baseline. All lymph nodes must be non-pathological in size (< 10 mm short axis).
Non CR/Non PD	Persistence of one or more NTL
Progression (PD)	Unequivocal progression of existing non-target lesions. Unequivocal progression may be due to an important progression in one lesion only or in several lesions. In all cases the progression MUST be clinically significant for the physician to consider changing (or stopping) therapy.

Not Evaluable (NE)	
Only relevant when one or some of the non-target lesions were not assessed and, in the Investigator's opinion, they are not able to provide an evaluable overall non-target lesion assessment at this visit.
 
Note: For subjects without target lesions at baseline, this is relevant if any of the non-target lesions were not assessed at this visit and the progression criteria have not been met.

--------------------	---

To achieve ‘unequivocal progression’ on the basis of non-target lesions, there must be an overall level of substantial worsening in non-target disease such that, even in presence of SD or PR in target lesions, the overall tumor burden has increased sufficiently to merit discontinuation of therapy. A modest ‘increase’ in the size of one or more non-target lesions is usually not sufficient to qualify for unequivocal progression status.

New Lesions

Details of any new soft tissue lesions will also be recorded with the date of assessment. The presence of one or more new lesions is assessed as progression.

A lesion identified at a follow-up assessment in an anatomical location that was not scanned at baseline is considered a new lesion and will indicate disease progression.

The finding of a new lesion should be unequivocal: i.e., not attributable to differences in scanning technique, change in imaging modality or findings thought to represent something other than tumor.

If a new lesion is equivocal, for example because of its small size, the treatment and tumor assessments should be continued until the new lesion has been confirmed. If repeat scans confirm there is a new lesion, then the progression date should be declared using the date of the initial scan.

Symptomatic deterioration

Symptomatic deterioration is not a descriptor of an objective response; it is a reason for stopping study therapy.

Evaluation of Overall Visit Soft Tissue Response

The overall visit response will be derived using the algorithm shown in [Table 14](#).

Table 14 Overall Visit Soft Tissue Response

Target lesions	Non-Target lesions	New Lesions	Overall soft tissue response
CR	CR	No	CR
CR	NA	No	CR

Table 14 Overall Visit Soft Tissue Response

Target lesions	Non-Target lesions	New Lesions	Overall soft tissue response
NA	CR	No	CR
CR	Non CR/Non PD	No	PR
CR	NE	No	PR
PR	Non PD or NE	No	PR
SD	Non PD or NE	No	SD
NA	Non CR/Non PD	No	SD (Non CR/Non PD)
NA	NA	No	NED
NE	Non PD or NE	No	NE
NA	NE	No	NE
PD	Any	Yes or No	PD
Any	PD	Yes or No	PD
Any	Any	Yes	PD

CR = complete response, PR = partial response, SD = stable disease, PD = progressive disease, NE = not evaluable, NA = not applicable (only relevant if there were no TL and/or NTLs at baseline), NED = No Evidence of Disease (only relevant when there is no TL and NTL from baseline).

Specifications for radiological imaging

These notes are recommendations for use in clinical studies. The use of standardized protocols for CT and MRI allows comparability both within and between different studies, irrespective of where the examination has been undertaken.

CT scan

CT scans of the chest, abdomen, and pelvis should be contiguous throughout all the anatomical regions of interest.

The most critical CT image acquisition parameters for optimal tumor evaluation using RECIST Version 1.1 are anatomic coverage, contrast administration, slice thickness, and reconstruction interval.

Anatomic coverage

Optimal anatomic coverage for most solid tumors is the chest, abdomen and pelvis. Coverage should encompass all areas of known predilection for metastases in the disease under evaluation and should additionally investigate areas that may be involved based on signs and symptoms of individual patients. Because a lesion later identified in a body part not scanned at baseline would be considered as a new lesion representing PD, careful consideration should be given to the extent of imaging coverage at baseline and at subsequent follow-up time

points. This will enable better consistency not only of tumor measurements but also identification of new disease.

Intravenous contrast administration

Optimal visualization and measurement of metastases in solid tumors requires consistent administration (dose and rate) of intravenous contrast as well as timing of scanning. Typically, most abdominal imaging is performed during the portal venous phase and (optimally) about the same time frame after injection on each examination. An adequate volume of a suitable contrast agent should be given so that the metastases are demonstrated to best effect and a consistent method is used on subsequent examinations for any given patient. It is very important that the same technique be used at baseline and on follow-up examinations for a given patient. For patients who develop contraindications to contrast after baseline contrast CT is done, the decision as to whether non-contrast CT or MRI (enhanced or non-enhanced) should be performed should also be based on the tumor type and anatomic location of the disease and should be optimized to allow for comparison to the prior studies if possible. Each case should be discussed with the radiologist to determine if substitution of these other approaches is possible and, if not, the patient should be considered not evaluable from that point forward. Care must be taken in measurement of TLs on a different modality and interpretation of non-target disease or new lesions, since the same lesion may appear to have a different size using a new modality. Oral contrast is recommended to help visualise and differentiate structures in the abdomen.

If iodine contrast media is medically contraindicated at baseline or at any time during the course of the study then the recommended methods are CT thoracic examination without contrast and abdominal and pelvic MRI with contrast. If MRI cannot be performed, then a CT scan without IV contrast is an option for the thorax, abdomen, and pelvic examinations. For assessment of brain lesions, MRI is the preferred method.

Slice thickness and reconstruction material

It is recommended that CT scans be performed at 5 mm contiguous slice thickness and this guideline presumes a minimum 5 mm thickness in recommendations for the measurable lesion definition. Exceptionally, particular institutions may perform medically acceptable scans at slice thicknesses greater than 5 mm. If this occurs, the minimum size of measurable lesions at baseline should be twice the slice thickness of the baseline scans.

All window settings should be included in the assessment, particularly in the thorax where lung and soft tissue windows should be considered. When measuring lesions, the TLs should be measured on the same window setting for repeated examinations throughout the study. All images from each examination should be included in the assessment and not “selected” images of the apparent lesion.

MRI scan

MRI has excellent contrast, spatial and temporal resolution; however, there are many image acquisition variables involved in MRI, which greatly impact image quality, lesion conspicuity and measurement. Furthermore, the availability of MRI is variable globally. The modality used at follow-up should be the same as was used at baseline and the lesions should be measured/assessed on the same pulse sequence. Generally, axial imaging of the abdomen and pelvis with T1 and T2 weighted imaging along with gadolinium-enhanced imaging should be performed. The field of view, matrix, number of excitations, phase encode steps, use of fat suppression and fast sequences should be optimized for the specific body part being imaged as well as the scanner utilized. It is beyond the scope of this appendix to prescribe specific MRI pulse sequence parameters for all scanners, body parts and diseases. Ideally, the same type of scanner should be used and the image acquisition protocol should be followed as closely as possible to prior scans. Body scans should be performed with breath-hold scanning techniques if possible.

For these reasons, CT is the imaging modality of choice.

FDG-PET scans

FDG-PET has gained acceptance as a valuable tool for detecting, staging and restaging several malignancies. If FDG-PET scans are included in a protocol, an FDG uptake period of 60 minutes prior to imaging has been decided as the most appropriate for imaging of patients with malignancy. Whole-body acquisition is important since this allows for sampling of all areas of interest and assessment if new lesions have appeared thus determining the possibility of interval progression of disease. Images from the base of the skull to the level of the mid-thigh should be obtained 60 minutes post injection. PET camera specifications are variable and manufacturer specific, so every attempt should be made to use the same scanner, or the same model scanner, for serial scans on the same patient. Whole-body acquisitions can be performed in either 2- or 3-dimensional mode with attenuation correction, but the method chosen should be consistent across all patients and serial scans in the clinical study.

PET/CT scans

At present, low dose or attenuation correction CT portions of a combined PET/CT are of limited use in anatomically based efficacy assessments and it is therefore suggested that they should not be substituted for dedicated diagnostic contrast enhanced CT scans for tumor measurements by RECIST Version 1.1. In exceptional situations, if a site can document that the CT performed as part of a PET/CT is of identical diagnostic quality to a diagnostic CT (with IV and oral contrast) then the CT portion of the PET/CT can be used for RECIST measurements. However, this is not recommended because the PET portion of the CT introduces additional data that may bias an Investigator if it is not routinely or serially performed.

ASSESSMENT OF BONE LESION PROGRESSION USING PCWG3 CRITERIA

Bone lesions will be assessed by bone scan in addition to being part of the RECIST v1.1 malignant soft tissue assessment.

Method of assessment

Bone lesions identified on a whole body isotopic bone scan at baseline should be recorded and followed by the same method as per baseline assessment.

In the D8731C00001 study isotopic bone scans will be used as a method of assessment to identify the presence of new bone lesions at follow-up visits. New lesions will be recorded where a positive and unequivocal hot-spot that was not present on the baseline bone scan assessment is identified on a bone scan performed at any time during the study. The Investigator should consider the positive hot-spot to be a significant new site of malignant disease and represent true disease progression in order to record the new lesion.

Tumor progression evaluation

Schedule of the evaluation

Baseline assessments should be performed no more than 28 days before the start of study treatment. The first follow-up assessment for Modules 1, 2, and 3 should be initially at 6 weeks (± 1 week) following the start of AZD4635 dosing and subsequent assessments will be performed every 2 cycles (8 weeks, ± 1 week) thereafter.

If an unscheduled assessment was performed and the subject has not progressed, every attempt should be made to perform the subsequent assessments at their originally scheduled visits. This schedule is to be followed in order to minimize any unintentional bias caused by some subjects being assessed at a different frequency than other subjects.

Documentation of lesions

All bone lesions (or sites of disease) should be identified by a bone scan at baseline. Their status should be followed at subsequent visits. At each visit an overall assessment of the bone lesion progression should be recorded by the Investigator. This section provides the definitions of the criteria used to determine and record bone progression at the investigational site at each visit.

Progression on a bone scan is identified using PCWG3 as follows:

- At the first bone scan post-baseline (6 weeks):
2 or more new metastatic bone lesions are observed on the first 6-week scan compared to the baseline assessment. The confirmatory scan, performed at least 6 weeks later and preferably no later than the next scheduled visit for a bone scan (i.e., Week 12), must show 2 or more additional new metastatic bone lesions (for a total of 4 or more new metastatic bone lesions since the baseline assessment) for progression to be documented.

Note - The first bone scan completed after baseline will be considered the ‘6-week scan’ regardless if taken at week 6 or at an unscheduled assessment.

- After the first bone scan post-baseline (6 weeks):
2 or more new metastatic bone lesions are observed compared to the 6-week assessment. The confirmatory scan, performed at least 6 weeks later and preferably at the next scheduled visit for a bone scan, must show the persistence of or an increase in the number of metastatic bone lesions compared to the prior scan for progression to be documented.

The date of progression is the date of the scan that first documents the second lesion.

Evaluation of bone progression status

Table 15 provides the definitions for the visit bone progression status for bone lesions.

Table 15 Bone progression status

Non Progressive Disease (Non-PD)	No evidence of progression, or appearance of one new bone lesion, or non-fulfillment of the progression criteria including new lesions without confirmation of progression.
Progressive Disease (PD)	Bone lesions fulfilling the requirements for at least 2 new lesions and confirmation of progression.
Not Evaluable (NE)	Only relevant if a follow-up bone scan is not performed

OVERALL RADIOLOGICAL VISIT ASSESSMENT

Table 16 provides the definitions how the visit responses for soft tissue (according to RECIST1.1 criteria) and bone progression status (according to PCWG3 criteria) are combined to give an overall radiological objective visit response.

Table 16 Overall radiological visit response

Overall visit soft tissue response (RECIST 1.1)	Bone progression status (PCWG3)	Bone lesions at visit Present/Absent	Overall radiological visit response
CR	Non-PD	Absent	CR
CR	Non-PD	Present	PR
CR	NE	-	PR
PR	Non-PD or NE	Any	PR
SD	Non-PD or NE	Any	SD
NED	Non-PD or NE	Any	Non-PD
NE	Non-PD or NE	Any	NE

Table 16 Overall radiological visit response

Overall visit soft tissue response (RECIST 1.1)	Bone progression status (PCWG3)	Bone lesions at visit Present/Absent	Overall radiological visit response
PD	Any	Any	PD
Any	PD	Any	PD

CR = complete response, PR = partial response, SD = stable disease, PD = progressive disease, NE = not evaluable, NED = No Evidence of Disease (only relevant when there is no TL and NTL from baseline).

CONFIRMATION OF RESPONSE

In the D8731C00001 study, imaging for confirmation of response (CR or PR) should be performed at the next scheduled RECIST and PCWG3 assessment, i.e., 8 weeks (and must not be less than 4 weeks later) following the date the criteria for response were first met.

Table 17 Best overall response when confirmation of CR and PR required.

Overall radiological response First time point	Overall radiological response subsequent time point	Best Overall response
CR	CR	CR
CR	PR	SD, PD or PR ^a
CR	SD	SD or PD
CR	PD	SD or PD
CR	NE	SD or NE
PR	CR	PR
PR	PR	PR
PR	SD	SD
PR	PD	SD or PD
PR	NE	SD or NE
NE	NE	NE

CR = complete response, PR = partial response, SD = stable disease, PD = progressive disease, NE = not evaluable.

^a If a CR is truly met at first time point, then any disease seen at subsequent time point, even disease meeting PR criteria relative to baseline, makes the disease PD at that point (since disease must have reappeared after CR). Best response would depend on whether minimum duration for SD was met. However, sometimes 'CR' may be claimed when subsequent scan suggest small lesions were likely still present and in fact the subject had PR, not CR at the first time point. Under these circumstances, the original CR should be changed to PR and the best response is PR.

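### Appendix G both includes bone lesions in the RECIST soft-tissue assessment and excludes them, so one new bone lesion on CT, X-ray or FDG-PET can be classed as PD or as Non-PD

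*Protocol*

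**What the plan says.** All places are in Protocol Appendix G unless stated.

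**Bone lesions outside RECIST.** The definition of non-target lesions (NTL) takes in all remaining lesions "except bone lesions which will be assessed as defined in bone lesion section of this appendix". The section on evaluating NTL repeats the exclusion: "All other lesions (or sites of disease), except for bone lesions, not recorded as TL should be identified as NTL at baseline". The New Lesions paragraph opens by speaking of soft-tissue lesions.

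**Bone lesions inside RECIST.** The section on bone progression begins: "Bone lesions will be assessed by bone scan in addition to being part of the RECIST v1.1 malignant soft tissue assessment". In the RECIST methods, under Plain X-rays: "Plain X-rays may be used as a method of assessment for bone NTLs and to identify the presence of new bone lesions". Under FDG-PET: "FDG-PET scans may be used as a method for identifying new lesions", subject to conditions on uptake and baseline imaging but with no exception for bone.

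**What each route does with one new lesion.** Under RECIST: "The presence of one or more new lesions is assessed as progression". Under PCWG3, Table 15 defines Non-PD as: "No evidence of progression, or appearance of one new bone lesion, or non-fulfillment of the progression criteria". Table 15 reserves PD for at least two new bone lesions with confirmation.

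**Imaging method for bone.** Section 8.1.2 of the core protocol allows bone scintigraphy or PET. The bone section of Appendix G names isotopic bone scans.

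**The concern.** No sentence says which rule governs a bone lesion seen on CT, X-ray or FDG-PET. The two rules have different thresholds: one new lesion under RECIST, two or more with confirmation under PCWG3. Section 8.1 counts progression when either the soft-tissue or the bone criterion is met, so the looser route prevails wherever a site uses it.

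The overlap is routine, because Section 8.1 expects both cross-sectional or PET imaging and a bone scan at each scheduled assessment. Section 8.1.1 assigns the RECIST visit response by program, so a bone focus entered as a new lesion would become PD automatically. Scans are reviewed at site, and central review is retrospective and optional.

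At stake are the rPFS event and its date, the end of DoR (which Section 9.4.4 ties to the PFS progression date) and, through confirmation of a PR, the primary ORR endpoint. Two sites with the same images could report different outcomes, and both would be following the protocol.

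**Working it through.** This is a classification rule, so the check is to trace one case through the protocol's tables under each reading.

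**Case A.** Target lesions SD, NTL not progressed, one unequivocal new bone lesion on CT, X-ray or FDG-PET, no other change.

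| Step | Bone lesion counts as a RECIST new lesion | Bone lesions excluded from RECIST |
|---|---|---|
| Soft tissue (Table 14) | PD (any new lesion) | SD |
| Bone status (Table 15) | Non-PD (one lesion) | Non-PD (one lesion) |
| Overall (Table 16) | PD (soft-tissue PD prevails) | SD |

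**Case B.** The same new lesion, at the visit meant to confirm a PR, with target lesions still PR.

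| Step | Counts | Excluded |
|---|---|---|
| Overall response at that visit | PD | PR |
| Best overall response (Table 17) | PR then PD: SD or PD, so not a confirmed response | PR then PR: confirmed PR |

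**Timing (Table 7, Section 8.1.2).**
- First post-baseline visit, Week 6: soft-tissue PD needs confirmation 4 to 8 weeks later, that is Week 6 + 4 = 10 to Week 6 + 8 = 14. Bone PD needs two new lesions at Week 6 and at least two more on a scan no earlier than Week 6 + 6 = 12.
- Second visit onwards: soft-tissue PD needs no confirmation. Bone PD needs at least two new lesions, with confirmation at least 6 weeks later.

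**Size per patient, at the planned numbers.**
- 6-month rPFS proportion: 1/30 = 3.3 points, if all 30 are followed to 6 months without censoring.
- ORR: 1/20 = 5 points. The synopsis gives 5/20 = 25% with an exact Clopper-Pearson interval of 8.7% to 49.1%, and this reproduces. Losing one responder gives 4/20 = 20%, interval 5.7% to 43.7%.

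The documents give no rate for isolated new bone lesions on these modalities, so no expected number of affected patients can be derived.

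**The case against.** The strongest reply is that the operative rules already settle the matter. Bone is excluded from NTL twice, the New Lesions paragraph begins with soft tissue, and the bone section makes bone scans the method for finding new bone lesions. The sentence that includes bone in RECIST could be read through the special case: "Lytic bone lesions or mixed lytic blastic lesions, with identifiable soft tissue components, can be considered measurable". A new lesion must also be unequivocal, and equivocal ones are followed until confirmed.

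This supports exclusion as the likelier intention. It does not remove the conflict. The inclusion sentence is not limited to lesions with a soft-tissue component, the X-ray paragraph names a category (bone NTLs) that cannot exist under exclusion, and nothing ranks one sentence above the other.

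Five stronger readings are tempting, and the documents do not support them:
- *Immediate PD from one focus at Week 6.* Table 7 requires confirmation of soft-tissue PD at that visit.
- *Baseline bone lesions kept as NTL would turn an overall CR into PR.* Table 16 already gives overall PR for a soft-tissue CR with bone lesions present, so the overall response is the same either way.
- *Bone-only patients would change outcome.* Their label may move between Non-PD and SD, but Section 9.4.4 treats both as not progressed, and Section 9.3 limits the tumor response population to measurable disease.
- *Any new FDG uptake counts.* The rule requires uptake more than twice that of surrounding tissue, and either absence on a baseline FDG-PET or a matching new CT/MRI lesion.
- *A stated share of patients would be misclassified.* The documents give no frequency.

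**Conclusion.** The inconsistency is in the current text and should be corrected. For the same images, the stated rules can give overall PD or overall SD, or a confirmed or an unconfirmed PR. Each patient affected is worth 3.3 points of 30 on the 6-month rPFS proportion or 5 points of 20 on ORR. The ORR effect arises only in a responder who has an isolated new bone lesion before or at the confirming visit.

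The conclusion assumes that the lesion is unequivocal, is seen on CT, X-ray or FDG-PET, and does not meet the PCWG3 bone criteria. At the first post-baseline visit the contrast is one lesion with soft-tissue confirmation against two lesions plus two more. From the second visit it is one lesion without confirmation against two or more with confirmation. How many patients would be affected is unknown.

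**What to change.** Choose one rule and state it once. The rule that fits the two NTL exclusions and Table 15 is this: bone lesions are not RECIST target, non-target or new lesions, whatever modality shows them, except for a measurable soft-tissue component of a lytic or mixed lesion; bone progression is judged only by the PCWG3 criteria, using the bone-imaging method the protocol names.

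Then make the text agree with it:
1. Amend the opening sentence of the bone progression section, which makes bone lesions part of RECIST.
2. Delete the Plain X-rays sentence on bone NTLs and new bone lesions.
3. Add the bone exception to the New Lesions and FDG-PET paragraphs.
4. Align Section 8.1.2 (bone scan or PET) with the bone section of Appendix G (isotopic bone scan), so that the method for bone is the same in both.
5. Carry the rule into the tumor eCRF guidance.

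The change is wording only and needs no extra scans, since bone imaging is already expected at each scheduled assessment. Its downside is that a single new bone lesion stays Non-PD until the PCWG3 criteria are met and confirmed, so some true progressions will be recorded later or not at all.
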